1.0 Objectives / Specific Aims

The objective of this project is to determine if 3D finger force training is an effective tool in restoring hand function post stroke.

Aim 1: Determine the effect of 3D finger force training on behavioral hand function

Hypothesis: Hand function will improve more in the experimental group than the control group.

Aim 2: Determine the effect of 3D finger force training on finger force direction control

Hypothesis: The experimental group will achieve greater ability to direct finger force than control after the training.

Aim 3: Determine the biomechanical mechanisms underlying improvement in force direction control

Hypothesis: The training results in improved muscular coordination.

2.0 Background

Our hands constitute our primary means of interacting with the external world. They allow us to dexterously manipulate objects such as tools, dishes, and smart phones. This exquisite manipulation requires precise generation of forces at the finger and thumb tips. Unfortunately, control of these forces can be profoundly impaired following stroke, thereby resulting in the object being mishandled, or not handled at all, and failure at task execution. Thus, hand function and use and utility of the entire upper extremity can be dramatically diminished, with ramifications for self-care, work, and leisure.

Both finger movement^{1,2} and force control³ are impaired after stroke. The central nervous system uses two separate neural strategies to control digit force generation vs. movement.⁴ Therefore, both neural strategies must be independently rehabilitated to achieve proper hand function. Clinical motor learning literature suggests that the best treatment modality involves training in volitional movements with explicit feedback. Current therapy focuses on training of volitional movement with explicit feedback.⁵ Unfortunately, digit force control is rarely explicitly addressed in therapy.

This gap in treatment is due to a lack of tools to provide explicit feedback on patients' volitional finger force generation. To address this unmet need, we developed a novel tool for practice of volitional three-dimensional (3D) force generation with explicit feedback.

3.0 Intervention to be studied: 3D finger force training (Fig 1)

Subjects will place their fingers into thimbles that are firmly attachable to the grip surfaces that are attached to force sensors (Fig 1).

Subjects in the experimental group will practice generating their finger force in various directions in 3D. Subjects will receive explicit visual feedback on force magnitudes in 3D in the computer screen (Fig 1).

The control group will practice 1D force generation with no explicit feedback on the non-target direction force, thus no feedback on directional control of force. This control condition is more accessible in clinic and cheaper, but does not provide explicit feedback for digit force direction that

is essential for successful object manipulation based on our preliminary data. This experimental vs. control comparison will determine the therapeutic value of the 3D force feedback vs. 1D.

[figure not shown]

Figure 1. Finger force training setup

Training will progress by varying posture requirements (toward forearm pronation, elbow extension, shoulder flexion,⁶ and whole body from seated to standing to walking⁷) and increasing finger force level,⁸ introducing feedback delay (to solicit increased reliance on intrinsic sensory feedback processing), and incorporating unilateral/bilateral training for both groups. External arm support may initially be provided (Fig 2A) but the extent of arm support will be reduced as the subject progresses. The whole body posture will progress from sitting to standing to walking with a harness for safety (Fig 2B), only if the participants can stand or walk without support. Regardless of the whole body posture, the training will be the finger force control (Fig 1).

[figure not shown]

Figure 2. Arm support (A) and harness (B)

There is no FDA approval on this finger force control training. The finger force training does not apply any energy to the subjects. The training setup measures subjects' voluntary finger force generation and provides visual feedback to the subjects on a computer screen (Fig 1).

5.0 Inclusion and Exclusion Criteria/ Study Population

Inclusion Criteria

- Age: 18 years old or older
- Survived a stroke at least 3 months ago
- Moderate to severe hand impairment (Chedoke-McMaster Hand Stage 2-4)
- Ability to generate palpable volitional grip force upon cue
- Sufficient cognitive ability to participate (NIH Stroke Scale, NIHSS, Questions and Commands score = 0-1)
- Ability to recognize all quadrants of the visual field (NIHSS Visual Field Test score = 0)

Exclusion Criteria

- Concurrent upper limb rehabilitation
- Inability to follow 2-step commands

- Severe muscle tone prohibiting passive movement of the fingers or proper placement of the fingers on the force sensors as needed to participate in the training (Modified Ashworth Scale, MAS=4-5 out of 5)
- Change in spasticity medication or botulinum toxin injection in the upper limb within 3 months prior to or during enrollment
- Total sensory loss on fingertips (NIHSS Sensory score=2)
- Comorbidity (e.g., orthopaedic conditions that limit ranges of motion, premorbid neurologic conditions)
- Language barrier or cognitive impairment that precludes providing consent

- **Screening:** Eligibility will be determined based on the potential participant's verbal disclosure or standardized clinical assessments. To minimize travel and face-to-face contact, video screening may also be used using HIPAA-compliant video applications (e.g., Microsoft Teams).
- **Sex/race/ethnicity:** We will include stroke survivors of all genders and all racial and/or ethnic groups that are representative of the demographics of Americans who had a stroke. We will not exclude people based on sex/gender, racial or ethnic group. We will aim to construct a participant pool that matches post-stroke survivor distributions in South Carolina. Our target enrollment for sex and race/ethnicity based on the demographic data and stroke surveillance data in South Carolina. This recruitment is possible, because we perform outreach to recruit stroke survivors of all sex, racial, and ethnic groups, as shown by our stroke registries currently having 48% female and 43% ethnic/racial minorities.
- **Children:** Children under the age of 18 years will be excluded. The rationale for exclusion of children is that stroke predominantly occurs in adults, and stroke is very rare in children. Importantly, these rare cases may actually differ in their etiology from the participants we propose to study.

6.0 Number of Subjects

A total of 60 subjects will be recruited.

7.0 Setting

All human subject involvement will take place at Ralph H. Johnson VA Medical Center.

8.0 Recruitment Methods

- We will get referrals from the VA Charleston Neuro Clinic. We will enroll participants upon discharge from usual-care therapy. The VA Charleston Neuro Clinic treats >300 new stroke cases every year.
- The IRB-approved VA stroke registry (IRB# 43107 "VA Stroke Rehabilitation Research Database") has contact and demographic information for 497 post-stroke Veterans who were seen at the Ralph H. Johnson VA Medical Center and are interested in participating in research. We will recruit from the VA stroke registry.

- A dedicated recruiter visits local clinics and performs community outreach to enroll patients into the RESTORE stroke registry supported by the NIH COBRE-funded Stroke Recovery Research Center (Pro#00037803). We will recruit from RESTORE.
- A chart review will be conducted for research purposes. Potentially eligible patients will be identified. We will submit a Research Data Request to obtain a recruitment report of MUSC patients who potentially meet eligibility criteria. The potentially eligible patients who have agreed to be contacted for future research by logging their MUSC Research Permissions preferences in MyChart will be contacted by phone, letter, or email and invited to participate. Other patients who did not update their MUSC Research Permissions in MyChart may also be cold-contacted by phone, letter, or email to be informed of the study if it is appropriate. We will not cold-contact any patients who have chosen to opt-out of receiving contact about research or who have met the maximum number of contact attempts at the time of recruitment.
- Similarly, potentially eligible patients in the VA medical records will be contacted by phone, letter, or email.
- In addition, advertisement via internet (e.g., South Carolina Research Studies Directory) will be used.

9.0 Consent Process

The consent process will take place in a private room when the potential participant comes to the laboratory on a scheduled time agreed upon between the study personnel and the participant. The content of the consent will be verbally explained to the participant and the participant will be asked to raise any questions and concerns. If the person requests a waiting period, then one will be given. If the person desires to consent immediately, then the person will provide consent immediately.

10.0 Study Design / Methods

- **Study design:** The study will be a randomized controlled trial. Subjects will be randomly assigned to either the experimental or control group using block randomization to ensure balance (half in the experimental, half in the control). Block sizes will be random (4, 6, or 8). The block randomization will be stratified equally by the moderate vs. severe impairment level (with the Fugl-Meyer Upper Extremity assessment cut-off score of 19⁹).
- **Intervention schedule:** All subjects will undergo approximately two-hour force training, 3 times per week for 6 weeks. The experimental group will practice for various target force direction to explore the 3D force workspace and receive explicit feedback in 3D force, while the control group will receive feedback in 1D on a computer screen (in target direction only with no explicit feedback on other directions, thus no training in force directional control, much like simple squeeze ball repetitions). The training dose will be controlled by having a minimum of 8 sets with 14 targets each (a total of 112 targets) per session, with maximum 30 sec allowed for each target (up to 56 min/session).
- **Evaluations:** Outcome measures will be assessed at baseline, immediately after 2 and 4 weeks of force training, at post (within a week after 6-wk force training), and 1 month after training ends (i.e. follow-up to assess retention). The baseline measurement will take place 3 times over 3 weeks prior to training to examine the baseline recovery rate. Each evaluation visit will take 1-5 hours. Evaluation for each outcome is detailed below.

- Behavioral hand function: Subjects' upper extremity function will be assessed using conventional clinical assessments used in occupational/physical therapy in which participants will be asked to move the affected hand and arm, grasp objects and perform prescribed tasks (e.g., lifting an object off the table, releasing the object into a bin, gripping hard, reaching as high or far as possible, opening the hand as much as possible). These tests will be videotaped for scoring. The joint positions and muscle activity during these tasks will also be recorded. The behavioral hand function assessments will last approximately 1 hr.
- Interview: Subjects will be interviewed after the completion of the intervention in a semi-structured interview format, to discuss the impact of the training on their day-to-day life. The interview will be audio-recorded. The interview will last approximately 30 min.

12.0 Data Management

- Recruitment projects are housed in REDCap. Only study personnel will have access to the REDCap database while actively enrolling for the study.
- Power analysis: The study was designed primarily to power the analysis of digit force direction. For the primary power analysis, based on previous studies, a clinically meaningful difference in force direction was deemed to be 6° . Reduction of force deviation to a value below $<20^\circ$ is expected to result in increased ability to manipulate objects.¹⁰ The mean force deviation for stroke survivors in Chedoke Hand Stage 2-4 is anticipated to be 25.6° based on our preliminary data.¹⁰ Therefore, a 6° change in force direction is expected to lead to a substantial functional improvement.

Our study is longitudinal with 4 primary time points. In the analyses, an autoregressive (AR(1)) covariance structure will be considered for the within-subject correlations (while other structures will also be examined). For a standard deviation of 6.6° (based on the force direction data in our preliminary study), an alpha level of 0.05, 90% power, and the AR(1) correlation between observations on the same subject of 0.8 (based on the preliminary study), a sample size of 22 participants per group will be adequate to detect a difference of 6° . Adjusting for an expected attrition rate of 15% and screen failure rate of 12%, a sample of 30 per group (for a total of n=60) is planned.

- Analysis: The primary formal analysis for the primary outcome measure will be a repeated measures general linear model with an AR(1) structure (although other structures will be considered and compared). The primary independent variables are group (experimental vs. control), evaluation time (baseline (3rd), 2, 4, and 6 weeks for the primary analyses; all 3 baselines and follow-up will be included in subsequent analyses), and their interaction (group \times evaluation time). In addition, we will include sex as an independent variable along with its interactions to study gender differences. If the group \times evaluation time interaction is significant, then the main alternative hypothesis of interest, that at 6 weeks there is difference between the two groups, will be tested using post-hoc tests. Greater improvement for the experimental than control group will support the hypothesis.

The time course of the effect will also be examined over the 6-week training period and at follow-up. As digit force direction will be recorded throughout the training sessions, spaghetti plots will be generated over the 18 training sessions along with evaluation sessions to examine a more detailed time course. Also in secondary analysis, other covariates such as initial impairment levels will be included. If missing data arise, multiple imputation methods will be applied under the assumption of missing at random (MAR).

The same analysis approach will be applied to each secondary outcome measure. Bonferroni correction will be applied to adjust for multiple comparisons. Data reduction methods may also be considered.

- **Qualitative Analysis:** Interviews will be audio recorded and transcribed verbatim. Qualitative data will be analyzed using the popular constructivist grounded theory methodology.^{11,12} The 'Framework Analysis' commonly used in applied qualitative research will guide the data analysis process¹³ and includes five key stages: familiarization, identifying a thematic framework, indexing, charting, mapping, and interpretation.^{14,15} Two researchers will conduct a high-level reading of transcripts to consolidate the data into analyzable units.¹⁴ Text segments ranging from a phrase to several sentences may be assigned codes a priori (e.g., areas of significance to this project). Additional codes will be created to capture new themes emerging from the data. Two researchers will independently read approximately 25% of the transcripts to establish inter-rater reliability for the final coding hierarchy that will be applied to analyze the all data. Disagreements in definitions or assignment of codes will be resolved through group discussion and further review of the data to achieve consensus. A thematic codebook will be created to document the final codes. Qualitative memos will be used throughout the analysis to document reflective notes, concepts and themes. Transcripts will be carefully read and coded with the assistance of qualitative data management software, constantly comparing the results against the original text for rigor.¹⁶ From final coded transcripts, text segments will be analyzed using a computational process of queries and comparisons.
- **Confidentiality:** All data except for the consent forms and HIPPA forms will be coded at the time of data recording such that personally identifiable information is not used in the data recording. Qualitative interviews will not have identifiable information such as participant names. Videos of the behavioral hand function will be recorded such that the hand, arm, and object being grasped will be in the video but not the participant face. All electronic data will be stored in a password-protected research server that is accessible to study personnel only. The server is backed up every day and maintained 24/7 by IT specialists. All paper data with personally identifiable information including the consent forms and HIPPA forms will be stored in a key-locked cabinet in a key-locked room that is accessible to study personnel only. Other paper data without personally identifiable information including testing sheets documenting testing sequences and notes will also be stored in a cabinet in a key-locked room that is accessible to study personnel only.
- **Data sharing:** Data will be shared with collaborating sites, Medical University of South Carolina (MUSC) and the VA Centralized Transcription Services Program. De-identified data will be shared with another collaborating site, North Carolina State University (NCSU). De-identified coded data will be reported and/or shared with the public and other investigators in publications, in ClinicalTrials.gov, or via network storage.

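### The primary model enters only the third baseline, and as a response visit; conditioning on baseline would sharpen the 6-week comparison, and the two earlier baselines may add a little more

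*Combined protocol and SAP*

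**What the plan says.** Section 10.0 (Evaluations) sets the pre-training schedule: "The baseline measurement will take place 3 times over 3 weeks prior to training to examine the baseline recovery rate". Section 12.0 (Analysis) specifies a "repeated measures general linear model with an AR(1) structure (although other structures will be considered and compared"), with group, evaluation time and their interaction as the main terms, plus sex and its interactions. Evaluation time has the levels "baseline (3rd), 2, 4, and 6 weeks for the primary analyses", and the same parenthesis adds that "all 3 baselines and follow-up will be included in subsequent analyses".

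The third baseline is therefore one of four response visits. Baseline force direction is not listed as a covariate in the primary model. If the interaction is significant, a post-hoc test compares the groups at 6 weeks, and greater improvement in the experimental group is taken as support. The plan does not say whether that test is a difference in 6-week means or in change from baseline. It gives no reason for using only the third baseline.

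**The concern.** Force direction is measured three times before training on every participant, so neither arm's training can have affected those values. Two features of the primary model leave some of that information unused.

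- **Baseline as a response with free means.** When each group has its own mean at each visit, the 6-week contrast is either a raw difference or a difference in change. Neither uses the baseline–outcome correlation as efficiently as conditioning on baseline does.
- **Only the third baseline enters.** If the measurement carries noise, or participants differ by a stable component, the two earlier values help to predict the week-6 value.

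The stake is precision of the main comparison in a trial planned on 22 evaluable participants per group. Nothing here biases the estimate.

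**Working it through.** **Inputs from section 12.0.** Difference 6°, SD 6.6°, alpha 0.05, power 90%, 22 per group, and "the AR(1) correlation between observations on the same subject of 0.8 (based on the preliminary study"). **Assumptions.** Two-sided test (sidedness is not stated); correlation 0.8 per 2 weeks; baselines at weeks −2, −1 and 0 (section 10.0 gives only three visits over three weeks); complete data; sex terms and the preceding interaction test ignored. Variances are in units of SD².

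**1. The plan's own figure.** For one time point, n = 2 × (6.6 × (1.960 + 1.282)/6)² = 25.43 per group. Multiply by the variance factor for a mean over repeated visits:
- AR(1) 0.8, three post-baseline visits: 25.43 × 0.831 = 21.1, so 22.
- AR(1) 0.8, four visits: 25.43 × 0.774 = 19.7, so 20.
- Constant correlation 0.8, four visits: 25.43 × 0.850 = 21.6, so 22.

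The 22 is reproduced, and 22/(0.85 × 0.88) = 29.4 gives 30 per group. None of this depends on which baselines enter the model.

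**2. The planned 6-week contrast under AR(1).** From the third baseline to week 6 is three 2-week steps, so the correlation is 0.8³ = 0.512.
- Raw 6-week difference: variance 1.
- Change from the third baseline: 2 × (1 − 0.512) = 0.976.
- Conditioning on the third baseline: 1 − 0.512² = 0.738.

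Conditioning cuts the variance of the change contrast by 1 − 0.738/0.976 = 24%. The non-centrality is 6/(6.6 × √v × √(2/22)) = 3.015/√v. By the non-central t:

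| Contrast | v | Non-centrality | df | Power |
|---|---|---|---|---|
| Raw difference | 1 | 3.015 | 42 | about 84% |
| Change | 0.976 | 3.05 | 42 | about 85% |
| Third baseline as covariate | 0.738 | 3.51 | 41 | 92.9% |
| Three baselines as covariates | 0.738 | 3.51 | 39 | 92.8% |

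**3. What the first two baselines add.** The residual variance of the week-6 value given a set of baselines is S_yy − S_yb S_bb⁻¹ S_by. The structures below other than AR(1) are assumptions that keep the 2-week correlation at 0.8.

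| Structure | Third only | All three | Reduction |
|---|---|---|---|
| AR(1) | 0.738 | 0.738 | 0% |
| AR(1) plus noise, reliability 0.95 to 0.85 | 0.678 to 0.498 | 0.675 to 0.457 | 0.4% to 8.3% |
| Stable component (share 0.2 to 0.7) plus AR(1) | 0.711 to 0.494 | 0.710 to 0.441 | 0.2% to 10.7% |
| Constant correlation 0.8 | 0.360 | 0.262 | 27.4% |

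The last row by hand: 1 − 0.64 = 0.360, and 1 − 3 × 0.64/2.6 = 0.262. Power there is 99.8% with one baseline and 99.99% with three. The benefit is an interval narrower by 1 − √(0.262/0.360) = 15%.

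**4. Why not average the three.** Under AR(1) the third baseline already carries all the pre-training information, so averaging dilutes it.
- Baselines one week apart: 1 − 0.4598²/0.9086 = 0.767, which is 4.0% above 0.738.
- Baselines treated as full AR(1) steps: 1 − 0.4164²/0.8311 = 0.791, which is 7.2% above.

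Separate covariates avoid this loss, because the fitted weights can move to the third value.

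**The case against.** The strongest reply is that the plan's lead structure is AR(1) with a correlation taken from preliminary data, and under it the earlier baselines add exactly nothing. That stands. A reader might infer from the constant-correlation figure that the plan forgoes 27% of its precision. The documents do not support this: the figure belongs to a structure that the plan leaves open but does not adopt, and to a setting where power is already above 99%.

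A reader might also infer that two baselines are thrown away. They are not. Section 12.0 brings them into later analyses, and section 10.0 gives them a purpose, the baseline recovery rate. The visit nearest the start of training is a natural, prespecified reference, particularly if there is a trend before training.

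It is also fair that adding two baseline visits with free means would not by itself improve the 6-week contrast, and that under AR(1) the whole gain comes from conditioning.

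These replies limit the size of the point but do not remove it. Section 12.0 allows other covariance structures. Exact AR(1) leaves no room for separate measurement error or a stable patient component. Conditioning on baseline improves on the planned contrast even when AR(1) holds. Separate covariates do not assume a flat baseline, so a pre-training trend is no obstacle.

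**Conclusion.** The point holds as a low-cost improvement in efficiency, not as an error. Under the plan's AR(1) 0.8, conditioning on baseline takes the 6-week contrast variance from 0.976 to 0.738 and power at 22 per group from about 85% to 93%. The two earlier baselines then add 0% under AR(1), about 0.2% to 11% under the mixed structures examined, and 27% only under constant correlation 0.8.

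These sizes rest on the assumed visit spacing, a two-sided test, complete data, and noise and stable-component shares that the documents do not give. Nor should a reader conclude from the 85% that the sample size is wrong. The stated 22 is reproduced by a calculation for a mean over visits, the plan does not name the contrast behind it, and it does not depend on this point.

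**What to change.** Before outcome data are examined, amend section 12.0 so that the primary model takes weeks 2, 4 and 6 as outcomes, with the three baseline values as separate covariates whose coefficients may differ by visit. Name the group difference at 6 weeks as the test and take it directly from that model. Once baseline is no longer a response, a treatment effect that is constant over weeks 2 to 6 would not appear in the group-by-time interaction, so that interaction should not gate the test.

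An equivalent option keeps all baselines as response visits with a mean common to both arms. There the covariance should not be forced to AR(1), or the earlier baselines receive no weight by construction.

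Keep the third-baseline-only model as a sensitivity analysis, and do not substitute a simple three-visit mean.

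The cost is plan wording and two degrees of freedom, about 0.1 point of power if AR(1) holds exactly. No visits are added. The plan must also say how a missed early baseline is handled; the multiple imputation already foreseen in section 12.0, or the common-mean version, would cover it.

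### Does adding sex and unspecified sex interactions to the primary-analysis paragraph leave the primary test undefined?

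*Combined protocol and SAP*

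**What the plan says.** Section 12.0 (Data Management, Analysis item) specifies a repeated measures general linear model with AR(1) covariance for the primary outcome, digit force direction. It defines the core of that model: "The primary independent variables are group (experimental vs. control), evaluation time", plus the interaction of the two. The next sentence is "In addition, we will include sex as an independent variable along with its interactions to study gender differences". After it comes the gate, which applies once the group-by-time term passes its test: "then the main alternative hypothesis of interest, that at 6 weeks there is difference between the two groups, will be tested using post-hoc tests".

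Later in the same section, further adjustment is placed elsewhere: "Also in secondary analysis, other covariates such as initial impairment levels will be included". Sex is not mentioned there.

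For its 6-degree target, the power paragraph concludes that "a sample size of 22 participants per group will be adequate to detect a difference of" that size, and its listed inputs include no sex term. On the sex mix, section 5.0 says "Our target enrollment for sex and race/ethnicity based on the demographic data and stroke surveillance data in South Carolina" without giving a number for the trial sample. The one share it states describes the recruitment sources: "as shown by our stroke registries currently having 48% female and 43% ethnic/racial minorities".

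**The concern.** The sex sentence sits inside the primary-analysis paragraph, directly ahead of the gating test. Studying gender differences in a treatment effect normally means fitting sex by group and sex by group by time. Once those terms are in the model there is no longer a single group-by-time effect. There is one per sex, and the overall test is some average of the two.

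The plan does not fix the weights. Equal weights and the observed sex distribution are both common, and software defaults differ. If the training works differently in women and men, these are different quantities, and the choice could be made after the data are seen. If enrolment is clearly unequal, equal weighting also costs precision that the sample size did not allow for. The later sentence that sends only other covariates to secondary analysis could be read as confirming that sex belongs in the primary model.

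**Working it through.** **Inputs.** From section 12.0: SD 6.6 degrees, AR(1) correlation 0.8, four primary time points, target difference 6 degrees, alpha 0.05, 22 per group. From section 5.0: 48% female in the registries. Assumptions: two-sided testing, equal spacing of the four visits, the same SD and sex share in both arms, and every female share other than 48%.

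**The plan's own figure.** The plan gives no formula or sidedness. One calculation that returns 22 is a two-sided normal comparison of the mean of the three post-baseline visits. Its variance factor is [3 + 2(0.8 + 0.8 + 0.64)]/9 = 0.831, so n = 2(1.960 + 1.282)² × 6.6² × 0.831/6² = 21.1, rounded up to 22. The match is not unique. For the inflation, 22/0.85 rounds up to 26 and 26/0.88 rounds up to 30, as stated.

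**Effect of the weighting on variance.** Let p be the female share and n the number per arm.

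- Observed weights: p² × 2/(np) + (1−p)² × 2/(n(1−p)) = 2/n. This equals the variance without sex terms, so nothing is lost.
- Equal weights: 0.25 × [2/(np) + 2/(n(1−p))] = (2/n) × 1/[4p(1−p)].

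At p = 0.48, 4p(1−p) = 4 × 0.48 × 0.52 = 0.998, a variance increase of about 0.2%.

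**6-week contrast (change from baseline).** The variance factor is 2(1 − 0.8³) = 0.976. Without sex terms the standard error is 6.6 × √(0.976 × 2/22) = 1.966. With equal weights it is 1.966/√[4p(1−p)]. Power for 6 degrees comes from the noncentral t distribution (42 df without sex terms, 40 df with them).

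| Model | 4p(1−p) | SE (degrees) | Power |
|---|---|---|---|
| No sex terms | – | 1.966 | 0.846 |
| Equal weights, 48% female | 0.998 | 1.968 | 0.845 |
| Equal weights, 40% (assumed) | 0.96 | 2.006 | 0.831 |
| Equal weights, 30% (assumed) | 0.84 | 2.145 | 0.779 |

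**Gating test (3 df).** Equal weighting multiplies the noncentrality by the same 4p(1−p). The level of power depends on the assumed time course whether or not sex is modelled, so only the change within each course matters here. At 48% female, power goes from 0.713 to 0.711 for a linear course, from 0.855 to 0.854 for a plateau from week 4, and from 0.987 to 0.986 for a single step. The largest change is 0.002.

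**Shift in the estimate.** If the effect differs by D degrees between the sexes, the two weightings differ by D(0.5 − p). With an assumed D of 6 degrees, as large as the whole target difference, that is 6 × 0.02 = 0.12 degrees at 48% female and 6 × 0.20 = 1.2 degrees at an assumed 30%.

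**Precision of by-sex effects.** At 48% female there are 22 × 0.48 = 10.56 women and 11.44 men per arm. The 95% half-width is 2.021 × 6.6 × √(0.976 × 2/n), where n is the number of that sex per arm: 5.74 degrees for women and 5.51 for men. Any by-sex result can only be descriptive.

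**The case for a change.** The strongest case for a change is that two analysts could fit different primary models and both claim to have followed the plan. The 48% describes registries rather than the trial sample, so the enrolled mix could be less even. Coding can also matter at an even mix. If sex interactions are fitted with one sex as reference and the group-by-time coefficients are read directly, they describe that sex alone. At 48% female the 6-week contrast would then have power of about 0.57 (men as reference) or 0.54 (women as reference), against 0.85. Closing the gap would take one sentence.

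Part of this stands: the plan does not list the interactions, and no other section does. The rest is weaker. Reading one sex's coefficient as the trial result would be an analyst's error, because the stated hypothesis is a difference between the two groups. The sentence about other covariates can simply mean covariates besides those already named, so it does not place sex in the primary test. An uneven mix costs power only under equal weights; averaging over the observed mix costs none. That one extra sentence would be cheap does not show that the plan as written gives a wrong answer.

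**Conclusion.** This is a gap in detail that a competent analyst fills sensibly, and it requires no change. The text gives the default: the primary variables are listed without sex, the gate is group by time, the 6-week hypothesis concerns the two groups, and sex is added for a separate stated purpose. An analyst can take the primary test from the model without sex-by-group terms, or average over the observed sex distribution. Under the equal-effect calculation both have the same variance, apart from a trivial loss of degrees of freedom.

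On the documented inputs, even equal weighting moves power by at most 0.002, and the estimate by 0.12 degrees under an assumed 6-degree sex difference in effect. This rests on a sex mix near 48% female, a common SD and similar shares in both arms. At an assumed 30% female, equal weighting would lower the power of the 6-week contrast to 0.78 and could shift the estimate by 1.2 degrees, but nothing in the documents points to that combination.
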